4 PARTICIPANT ENTRY

4.1 PRE-RANDOMISATION EVALUATIONS

Potential subjects for the study will be recruited from hospital outpatient clinics, GP surgeries, spirometry sessions/clinics, other research projects, and advertisements. They will attend the respiratory clinic at St Mary's Hospital, where the outline of the study will be explained to them and a Participant Information Sheet (PIS) provided. They will be given the opportunity to ask questions and be informed that their participation is voluntary. Subjects may decide they wish to have more time to consider taking part in the study, in which case a follow up appointment will be made, or they may continue with the screening process. When a subject has had enough time to consider their participation in this study, and only when they have agreed to take part, they will be asked to read, sign and date a consent form in the presence of the investigator who will also sign the consent form. A copy will be kept in the research file, a copy given to the patient and a copy put into their medical notes.

After signing a consent form, eligible subjects will undergo screening. Screening involves taking a medical history and examination, lung function testing, a histamine challenge, FeNO levels, skin prick testing, blood tests, a urine pregnancy test, and a chest radiograph to assess suitability against the defined inclusion and exclusion criteria. Blood tests include general screening for underlying illness, specifically full blood count, urea and electrolytes, liver function tests, coagulation, and C-reactive protein (CRP), as well as serology for rhinovirus 16 (RV-16). They will be matched to the inclusion/exclusion criteria, which have been maintained from previous studies using the rhinovirus-induced asthma exacerbation model.

4.2 INCLUSION CRITERIA

- Age 18-55 years
- Male or female
- Clinical diagnosis of asthma for at least 6 months prior to screening
- An Asthma Control Questionnaire (ACQ) Score >0.75
- Positive histamine challenge test ($PC_{20} < 8 \mu\text{g/ml}$, or $< 12 \mu\text{g/ml}$ and bronchodilator response $\geq 12\%$)
- Worsening asthma symptoms with infection since last change in asthma therapy
- Positive skin prick test to common aeroallergens (e.g. animal epithelia, dust mite)
- Treatment comprising inhaled corticosteroids (ICS) or combination inhaler (Long-Acting Beta Agonist with ICS), with a daily ICS dose of at least 100mcg fluticasone or equivalent.
- Participant is willing for their GP to be informed of their participation.
- English speaker

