3.1 STUDY OUTCOME MEASURES

Primary outcome:

- Difference in Total Lower Respiratory Tract Symptoms Score after RV infection (sum of daily scores day 0 to day 14) between OC459 and placebo groups.

Secondary outcomes:

- Difference between OC459 and placebo groups in the following (all measured as peak and change from baseline):
 - Increase in ACQ score (health status)
 - Reduction in Forced Expiratory Volume in 1 second (FEV₁) or Peak Expiratory Flow (PEF) on spirometry
 - Increase in FeNO
 - Decrease in PC₂₀
 - Virus load in nasal lavage – total (area under the curve) for days 2-5+7+10, as well as peak and difference from baseline
 - Increase in sputum eosinophilia
 - Leukocyte numbers (e.g. ILC2, Th2) in FACS-sorted BAL, serum and nasal scrapes, and in immunohistochemistry-stained biopsies
 - Cytokine levels (e.g. IL-4, IL-5, IL-13) in nasosorption, nasal lavage, bronchosorption, BAL
 - mRNA expression of same cytokines in cells in BAL and bronchial biopsies
 - In *ex vivo* studies, protein and mRNA levels of antiviral cytokines (e.g. IFN- α , IFN- λ) produced by cells from blood, BAL, and bronchial brushings in response to rhinovirus infection
- Difference in number of adverse events in OC459 and placebo groups

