9.6 HISTAMINE CHALLENGE (PC₂₀)

Histamine challenge (maximum concentration 16 mg/mL) will be performed according to American Thoracic Society (ATS) guidelines by using the 2 minute tidal breathing method [24]. The provocative concentration of histamine causing a 20% reduction in FEV₁ (PC₂₀) is then calculated.

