4.3. Study Population

English speaking, male or female patients between the age of 18-55 who have had a Clinical diagnosis of asthma for at least 6 months prior to screening will be deemed eligible for the trial if they satisfy the following additional Inclusion Criteria:

- An Asthma Control Questionnaire (ACQ-6) Score >0.75
- Positive histamine challenge test (PC_{20} <8 $\mu\text{g}/\text{ml}$, or <12 $\mu\text{g}/\text{ml}$ and bronchodilator response $\geq 12\%$)
- Worsening asthma symptoms with infection since last change in asthma therapy
- Positive skin prick test to common aeroallergens (e.g. animal epithelia, dust mite)
- Treatment comprising inhaled corticosteroids (ICS) or combination inhaler (Long-Acting Beta Agonist with ICS), with a daily ICS dose of at least 100mcg fluticasone or equivalent.
- Participant is willing for their GP to be informed of their participation.

Patients must also not fall under any of the following exclusion criteria:

- Presence of clinically significant diseases other than asthma (cardiovascular, renal, hepatic, gastrointestinal, haematological, pulmonary, neurological, genitourinary, autoimmune, endocrine, metabolic, neoplasia etc.), which, in the opinion of the investigator, may either put the patient at risk because of participation in the trial, or diseases which may influence the results of the study or the patient's ability to take part in it
- Smoking history over past 12 months.
- Seasonal allergic rhinitis symptoms at screening or during the 3 week run-in (prior to rhinovirus inoculation).
- Asthma exacerbation or viral illness within the previous 6 weeks or during the 3 week run-in (prior to rhinovirus inoculation).
- Current or concomitant use of oral steroids, anti-leukotrienes or monoclonal antibodies.
- Pregnant or breast-feeding women. Patients should not be enrolled if they plan to become pregnant during the time of study.
- Contact with infants <6 months or immunocompromised persons, elderly and infirm at home or at work.
- Subjects who have known evidence of lack of adherence to medications and/or ability to follow physician's recommendations.

Whilst not listed within the trial protocol; an additional test was carried out to assess previous exposure to rhinovirus 16, as evidenced by the presence of serum neutralising antibodies to rhinovirus 16 at screening.

Subjects who meet the relevant criteria and provide informed consent are deemed eligible for randomisation to the trial.

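### The PC20 entry cut-offs are printed in µg/ml, but the challenge that yields PC20 is specified to 16 mg/mL; the units differ 1000-fold and must be reconciled

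*Protocol*

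**What the plan says.** Three sections bear on the point.

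- Protocol 4.2 lists a "Positive histamine challenge test" among the inclusion criteria. The first route is a PC20 below 8 µg/ml. The second is written "or $< 12 \mu\text{g/ml}$ and bronchodilator response $\geq 12" per cent.

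- SAP 4.3 restates the criterion with the same two numerals and the same unit. Its second route reads "or <12 $\mu\text{g}/\text{ml}$ and bronchodilator response $\geq 12" per cent.

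- Protocol 9.6 describes the test: "Histamine challenge (maximum concentration 16 mg/mL) will be performed according to American Thoracic Society (ATS) guidelines". It goes on: "The provocative concentration of histamine causing a 20% reduction in FEV₁ (PC₂₀) is then calculated". PC20 is therefore a histamine concentration obtained from this challenge, whose only stated concentration is in mg/mL.

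Neither document gives a starting concentration, a dilution series, a conversion between the units, or a unit for the recorded PC20 apart from the one attached to the entry cut-offs. PC20 has other uses as well. Protocol 3.1 lists "Decrease in PC₂₀" as a secondary outcome, SAP 6.1 lists PC20 as a baseline characteristic, and SAP 7.3.3 uses it in the correlations.

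**The concern.** An entry threshold and the test that it is applied to should be on one scale. Here the threshold is in a unit 1000 times smaller than the one used for the test, and nothing in either document explains the change. Protocol 4.1 makes the histamine challenge part of screening against the inclusion criteria, so this is a working decision rule and not background text.

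Two things are at stake. The first is the definition of the population. A cut-off of 8 or 12 µg/ml describes people far more responsive to histamine than a cut-off of 8 or 12 mg/mL does, so a reader of the plan cannot tell which group the trial set out to enrol.

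The second is the classification of deviations. Someone checking a subject's PC20 against the printed criterion could call that subject ineligible when the screening team, working in the challenge's unit, had judged the subject eligible. SAP 5.3 removes major protocol deviations from the per-protocol set, and SAP 7.3.1 gives more weight to conclusions on which the per-protocol and full analysis sets agree. An unresolved unit could therefore reach the supporting analyses.

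**Working it through.** The plan derives no figure here that could be reproduced. The check is a unit conversion and a comparison of the sections.

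**Inputs**

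- Cut-offs: 8 and 12 µg/ml (Protocol 4.2; repeated in SAP 4.3).
- Maximum challenge concentration: 16 mg/mL (Protocol 9.6).
- 1 mg = 1000 µg.

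**Step 1: one scale.** 16 mg/mL × 1000 = 16,000 µg/mL. Conversely, 8 µg/ml = 0.008 mg/mL and 12 µg/ml = 0.012 mg/mL.

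**Step 2: distance of each cut-off from the maximum.** The ratio is maximum ÷ cut-off, and the number of doublings is log2 of that ratio.

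| Reading | Cut-off | Maximum ÷ cut-off | Share of maximum | Doublings below maximum |
|---|---|---|---|---|
| As printed (µg/ml) | 8 | 16,000 / 8 = 2000 | 0.05% | log2(2000) = 10.97 |
| As printed (µg/ml) | 12 | 16,000 / 12 = 1333 | 0.075% | log2(1333) = 10.38 |
| Same numeral in mg/mL | 8 | 16 / 8 = 2 | 1/2 | log2(2) = 1.0 |
| Same numeral in mg/mL | 12 | 16 / 12 = 1.33 | 3/4 | log2(1.33) = 0.42 |

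The factor of 1000 is the ratio between the units. The factors of 2000 and 1333 are the ratios of the stated maximum to the stated cut-offs. They answer different questions and should not be interchanged.

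**Step 3: who is affected by the choice of reading.** A subject with PC20 below 0.008 mg/mL meets the criterion on either reading. Between 0.008 and 0.012 mg/mL, the literal reading admits the subject only with a bronchodilator response of at least 12%. At 0.012 mg/mL and above, the literal reading excludes everyone, whereas the mg/mL reading still admits all subjects below 8 mg/mL and, with the bronchodilator response, those below 12 mg/mL. The documents give no PC20 distribution, so the number of subjects in these bands cannot be computed.

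**Step 4: where the criterion enters the analysis.**

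- The full analysis set (SAP 5.2) is defined by randomisation, inoculation, confirmed infection and completion of at least 14 days after inoculation. It has no PC20 condition.
- The sample size (Protocol 10.1, SAP 4.4) uses the difference and standard deviation of the symptom score, error rates, infection success and drop-out. PC20 does not enter.
- The per-protocol set (SAP 5.3) depends on major deviations, which are to be defined before database lock and without knowledge of treatment. This is the one analysis set that an eligibility reading could change.

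**The case against.** The strongest case on the other side accepts the mismatch and disputes its consequences.

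- *A maximum is only an upper bound.* A cut-off far below 16 mg/mL does not contradict it logically. This stands. A reader might infer that the criterion cannot be met as printed. The documents do not support that, because they do not say where the concentration series starts.
- *The main result is safe.* A reader might infer that the primary comparison or the power is compromised. Neither is: the full analysis set and the sample size make no use of PC20. This stands in full.
- *Exclusion from the per-protocol set is not automatic.* A reader might infer that every subject entered on an mg/mL reading would be a deviation and would be removed. That goes too far in two ways. Subjects below the literal cut-off meet both readings. And only deviations that could confound interpretation count as major, which leaves the blinded review room to settle an evident unit problem.
- *The secondary outcome uses measured values, not the cut-off.* This is correct. The mismatch does not by itself disturb the PC20 comparison, and nothing in the documents suggests that values were recorded in mixed units.
- *In practice nobody would be misled.* Protocol 4.1 says that the criteria were carried over from earlier studies with this model, and the numerals 8 and 12 sit naturally beside a maximum of 16. That makes misapplication less likely. It does not show which section is wrong, and a criterion that has to be read against its own wording still needs correcting.

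A misreading of the page does not explain the mismatch. The microgram unit is printed twice in each document, and the mg/mL in Protocol 9.6 is clear.

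**Conclusion.** The point holds as an inconsistency in a decision threshold. The entry cut-offs and the challenge are stated in units that differ by a factor of 1000, with no explanation. Taken literally, the cut-offs lie about 11.0 and 10.4 doublings below the challenge maximum; on the challenge's scale they would lie 1.0 and 0.4 doublings below it. Those are very different populations.

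The consequence is limited. Subjects whose PC20 is at or above the literal cut-off could be classed as eligibility deviations and could leave the per-protocol set if the blinded review judges the deviation major. That is a risk, not a certainty, and the documents do not allow the number of subjects to be calculated.

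This conclusion rests on one assumption, which Protocol 9.6 supports: that the PC20 used for eligibility comes from the challenge described there. A reader might go further and treat the microgram unit as a plain misprint and Protocol 9.6 as correct. The documents do not establish that, and this review takes no position on which unit or threshold is right.

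**What to change.** The sponsor should reconcile Protocol 4.2, SAP 4.3 and Protocol 9.6 so that the entry threshold, the challenge range and the recorded PC20 share one stated unit. Protocol 4.1 says that the criteria were taken over from previous studies, so the source should be available to check. Stating the concentration series in Protocol 9.6, and the PC20 unit where the SAP lists it as a baseline variable and an outcome, would close the gap.

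Eligibility deviations should then be judged against the reconciled criterion, with that decision recorded in the blinded definition of major deviations before database lock.

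The cost is a short correction in two documents. No analysis, sample size or visit changes.

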4.3 EXCLUSION CRITERIA

- Presence of clinically significant diseases other than asthma (cardiovascular, renal, hepatic, gastrointestinal, haematological, pulmonary, neurological, genitourinary, autoimmune, endocrine, metabolic, neoplasia etc.), which, in the opinion of the investigator, may either put the patient at risk because of participation in the trial, or diseases which may influence the results of the study or the patient's ability to take part in it
- Smoking history over past 12 months.
- Seasonal allergic rhinitis symptoms at screening or during the 3 week run-in (prior to rhinovirus inoculation).

- Asthma exacerbation or viral illness within the previous 6 weeks or during the 3 week run-in (prior to rhinovirus inoculation).
- Current or concomitant use of oral steroids, anti-leukotrienes or monoclonal antibodies.
- Pregnant or breast-feeding women. Patients should not be enrolled if they plan to become pregnant during the time of study participation (see note regarding contraception below).
- Contact with infants <6 months or immunocompromised persons, elderly and infirm at home or at work.
- Subjects who have known evidence of lack of adherence to medications and/or ability to follow physician's recommendations.

Contraception: To prevent pregnancy, male subjects with female partners of child bearing potential and female subjects must use at least two forms of adequate contraception for the entire duration of study participation. Adequate contraceptive precautions include:

1. Established use of oral, injected or implanted hormonal methods of contraception.
2. Placement of an intrauterine device (IUD) or intrauterine system (IUS).
3. Barrier methods of contraception: condom or occlusive cap (diaphragm or cervical/vault caps) with spermicidal foam/gel/film/cream/suppository.
4. Male sterilisation (with the appropriate post-vasectomy documentation of the absence of sperm in the ejaculate).

Men whose partners are already pregnant must continue to use contraception i.e. a condom during the trial and for three months thereafter. The chosen contraception method(s) must be followed from the first Investigational Medicinal Product (IMP) administration until at least 3 months after receiving the last dose of the IMP.

Sperm donation: Male subjects must not donate sperm throughout the study and for at least 3 months after the final dose of IMP.

4.4 WITHDRAWAL CRITERIA

Participants will be free to discontinue trial medications at any point during the study without giving reason. Where possible, follow up will continue. If a participant chooses to withdraw consent, data up to the point of self-withdrawal will be included unless the participant chooses otherwise.

Investigators will withdraw any subject if they are unable to tolerate the study medications, or if the a research investigator feels this is necessary or appropriate. In all cases, the reason for withdrawal must be recorded on the case report form and in the subject's medical records. Subjects will be closely monitored by the Clinical Research Fellow. This is defined further in the section on 'Serious Adverse Events'.

Subjects who are considered evaluable (i.e. confirmed rhinovirus infection) with sufficient data to assess the primary endpoint (i.e. complete diary cards of symptoms up to day 14 post-rhinovirus infection) will be included in the analysis. Subjects who are either withdrawn from the trial or who chose to discontinue participation and do not meet these criteria will be replaced until a sufficient number of evaluable subjects are reached (n=20).

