Secondary outcomes: measures of health status, lung function, airway hyper-responsiveness, exhaled nitric oxide (FeNO) levels, virus load, and other laboratory parameters (e.g. differential cell counts, levels of cytokine/biomarker proteins and mRNA in respiratory samples).

[figure not shown]
POPULATION 44 adults with asthma (of which 30 will be evaluable).

ELIGIBILITY Adult subjects with moderate persistent asthma who meet the inclusion/exclusion criteria described.

TREATMENT OC459 or placebo, for a total of 5 weeks per subject.

DURATION 27 months

FIGURE: STUDY OVERVIEW

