5 RANDOMISATION AND ENROLMENT PROCEDURE

5.1 RANDOMISATION PRACTICALITIES

Subjects who meet the relevant criteria and provide informed consent will be randomised to either OC459 or placebo in a 1:1 ratio. Randomisation will occur at a baseline visit after the screening visit(s), and will be in blocks of four in order to balance the number of patients allocated to each treatment group. An unblinded randomisation list (taking into account the blocking requirements) will be generated by Sealed Envelope Ltd and entered into the study database. This file will be password protected, with unblinding instructions provided by the database development team to the investigators.

At randomisation, the database will be interrogated and each new subject assigned the next sequential randomisation item on the list. The unblinded randomisation list will also be provided to the manufacturer, Atopix Ltd, in order to label IMP/placebo appropriately prior to dispensing to pharmacy. Thus the investigators, pharmacy and subjects will all be blinded.

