10 STATISTICS AND DATA ANALYSIS

10.1 SAMPLE SIZE CALCULATION

The sample size determination is based on the following assumptions:

Type I error probability $\alpha = 5\%$

Effect size = $(\mu_1 - \mu_0)/\sigma$, where

μ_i = mean PEP in group i ($i=1$: OC459, $i=0$: placebo),

σ = standard deviation of PEP, and

PEP is primary end-point (=total daily lower respiratory symptom scores over d0 to d14).

Based on a previously completed trial with similar design conducted at the same study site [10], σ is estimated to be 21.15 and the effect size equal to 22.21, yielding $n=15$ evaluable subjects per treatment group at 80% power. This is grossed-up for 80% rhinovirus inoculation success and adjusted for expected drop-outs to yield 22 enrolled patients per treatment group.

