4.7. Withdrawal and Replacement

Subjects who are considered evaluable (confirmed rhinovirus infection) and have completed at least 14 days post inoculation with RV-16 will be included in the analysis. Subjects lost to follow up will not be replaced if they were evaluable with sufficient data to assess the primary outcome. Subjects who are either withdrawn from the trial or who chose to discontinue participation and do not meet these criteria will be replaced until a sufficient number of evaluable subjects are reached (n=30).

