7.2. Primary Analysis

Uncorrected lower respiratory symptom scores collected from D0 to D14 will be aggregated to create an overall total for each patient. Where patient scores are missing, data will be imputed based upon rules set within Section 7.5. Patients missing $\geq 20\%$ of score data will be excluded from any additional per-protocol analyses.

Data will be presented using summary statistics per treatment group and will include median and interquartile range (IQR). A supplementary plot showing individual measurements for both groups with a box & whisker overlay showing median and IQR will be produced.

Primary analysis to test for difference between the mean aggregated scores of the two treatment groups will be carried out using Mann-Whitney U tests. Differences will be considered significant at $P < 0.05$. All P values are two-sided.

An additional secondary analysis will take place correcting the scores for bronchoscopy-related symptoms. Full methodology will be clarified within Section 7.3.1 below.

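### The protocol's replacement target of 20 evaluable subjects contradicts the 30 its own sample size requires, so the rule does not protect the planned power if losses exceed plan

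*Protocol*

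**What the plan says.** **Replacement target.** Protocol 4.4 (Withdrawal Criteria) says that subjects who withdraw or discontinue without being evaluable "will be replaced until a sufficient number of evaluable subjects are reached (n=20". Protocol 9.17 (Loss to Follow-up) repeats the same target for subjects lost to follow-up. SAP 4.7 has nearly the same rule with a different number: such subjects "will be replaced until a sufficient number of evaluable subjects are reached (n=30".

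**Number required.** Protocol 10.1 states: "σ is estimated to be 21.15 and the effect size equal to 22.21, yielding $n=15$ evaluable subjects per treatment group at 80% power". It then inflates this for 80% infection success and for drop-outs, to 22 enrolled per group. The protocol's Study Summary gives the population as "44 adults with asthma (of which 30 will be evaluable". SAP 4.4 repeats the calculation, and SAP 5.2 says that the evaluable subjects are the basis of the power calculation.

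**Who counts as evaluable.** Protocol 4.4 and 9.17 require confirmed infection and complete diary cards to day 14. SAP 4.7 and 5.2 require confirmed infection and at least 14 days completed after inoculation. For subjects lost to follow-up, SAP 4.7 also asks for sufficient primary-outcome data, without saying what is sufficient. SAP 7.2 and 7.5 impute missing daily scores.

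**The concern.** A replacement rule is there to protect the analysed sample size when losses run above plan. This one stops protecting it ten subjects short of the number on which the power statement rests. The figure stands in both of the protocol's replacement rules, so it is not a single stray digit, and the protocol contradicts itself as well as the SAP.

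At stake is the power of the primary comparison. The site works from the protocol during recruitment, and an analysis plan cannot later restore subjects who were never replaced. The two definitions of evaluable add to the problem. A subject with one missed diary day could be non-evaluable under the protocol, and so replaced, yet belong to the full analysis set under the SAP. The two documents can therefore count differently as well as aim at different totals.

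**Working it through.** **Inputs.** SD 21.15, difference 22.21, 15 evaluable per group, 80% power and type I error 5% (Protocol 10.1); 1:1 allocation (Protocol 5.1); two-sided testing and Mann-Whitney as the primary test (SAP 7.2); 80% infection and 22 enrolled per group (Protocol 10.1). The drop-out rate is not given.

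The sample-size text defines the effect size as a standardised ratio, but 22.21 works only as a raw difference in score points, since 22.21 standard deviations would need 1 subject per arm. I take it as raw: d = 22.21 / 21.15 = 1.050.

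**Step 1: reproduce the stated number.** n per arm = 2 × (1.960 + 0.842)² / 1.050² = 14.24, rounded up to 15. This matches the plan. A one-sided test would give 12, so the two-sided reading is the one that fits.

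**Step 2: power by number evaluable.** For a two-sided t-test with n per arm, power comes from the noncentral t distribution with 2n − 2 degrees of freedom and noncentrality d × √(n/2). At n = 10 the noncentrality is 1.050 × √5 = 2.348, against a critical value of 2.101. At n = 15 it is 2.876 against 2.048. Mann-Whitney power was simulated with normal data.

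| Evaluable (equal split) | t-test power | Mann-Whitney power |
|---|---|---|
| 30 (15 per arm) | 79.3% | about 76% |
| 26 (13 per arm) | 72.9% | not run |
| 22 (11 per arm) | 64.9% | not run |
| 20 (10 per arm) | 60.3% | about 55% |

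The normal approximation gives 82.0% at 15 per arm and 65.1% at 10. An 8:12 split of 20 gives 58.6% by t-test. The difference detectable with 80% t-test power rises from 22.4 points at 15 per arm to 28.0 at 10.

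**Step 3: what enrolling 44 should yield.** Expected infections: 44 × 0.80 = 35.2. Per arm, 22 × 0.80 = 17.6, and 15 / 17.6 = 0.852, so the implied drop-out is about 15%. Then 35.2 × 0.85 = 29.9, or about 30 evaluable, without any replacement.

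**Step 4: losses that would reach the gap.** With 35.2 infected:

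- 26 evaluable means 26 / 35.2 = 74% retained, or 26% drop-out.
- 22 means 62.5% retained, or 37.5% drop-out.
- 20 means 57% retained, or 43% drop-out.

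Lower infection has the same effect. As illustrative assumptions with 15% drop-out, 70% infection gives 44 × 0.70 × 0.85 = 26.2, and 60% gives 22.4.

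**Step 5: how likely a shortfall is.** Assume each enrolled subject independently has a 15/22 chance of being evaluable. The number evaluable from 44 is then binomial with mean 30. The chance of fewer than 30 is about 43%; the chance of 20 or fewer is about 0.15%.

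**Step 6: can 20 be read another way?** As a total it is ten short. As 20 per group (40 in total) it exceeds both the 30 required and the roughly 35 infections expected from 44.

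**The case against.** A reader might infer that following the protocol would itself cut power to about 55–60%. The documents do not support that. Protocol 4.4 and 9.17 govern only the replacement of subjects who are withdrawn or lost. Neither ends recruitment at 20, and enrolment is fixed separately at 44 (Study Summary, Section 3, Section 10.1). A site that follows the whole protocol enrols 44 and should have about 30 evaluable. Ending at 20 would take about 43% drop-out among the infected, or a site mistaking 20 for the recruitment target. This part of the objection stands: the 55–60% figure is a remote worst case.

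It can also be said that SAP 4.7 already gives 30, so the intention is clear and 20 is a wording error. That is fair as to intention, and it makes the correction uncontroversial. It does not remove the need for it, because the site's replacement decisions are taken under the protocol.

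Two further inferences also go too far. One is that a null result at 10 per arm could not be interpreted: an estimate and interval would still be informative, only less precise. The other is that the fix can never take enrolment above 44: Step 5 shows that a shortfall below 30 is quite possible. The mismatch over diaries is valid but separate, and the power figures do not depend on it.

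**Conclusion.** Wrong as written. The target of 20 in Protocol 4.4 and 9.17 contradicts the 30 in Protocol 10.1, the Study Summary and SAP 4.7, and no reading reconciles them.

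The consequence is a missing safeguard, not an expected loss of power. Between 20 and 29 evaluable the protocol asks for no replacement where the SAP does, and there is little slack because the expected yield from 44 is only just 30. Within that gap t-test power falls from 79% towards 60%, and the planned Mann-Whitney test from about 76% towards 55%. A modest shortfall is plausible; the bottom of the range is not.

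These figures rest on 22.21 being a raw difference, normal data with equal SDs, near-equal arms, and the implied 15% drop-out. The 43% and 0.15% also need the binomial assumption.

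**What to change.** - Change 20 to 30 (15 per arm) in Protocol 4.4 and 9.17, to match SAP 4.7 and Protocol 10.1.
- Use one definition of evaluable in Protocol 4.4 and 9.17 and SAP 4.7 and 5.2. State whether a diary with some missing days to day 14 qualifies, given that the SAP imputes such days.
- While editing, say whether a subject who completes without becoming infected is replaced. Both documents' replacement wording speaks of withdrawn, discontinued or lost subjects, so this is not explicit.

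The cost is a protocol amendment and a matching line in the SAP. On the documents' own assumptions the planned 44 need not change. If losses exceed plan, enrolment may go somewhat above 44, with the extra time and subject burden that brings; SAP 4.7 already commits to this.
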